### **3.2.4 Mapping of assessments performed at early discontinuation**

Unlike other scheduled visits, an early discontinuation visit (EDV) doesn't have a predetermined visit window and can occur at any days during the study. If an EDV occurs at the day of a scheduled visit, assessments (in-clinic safety assessments such as vital signs, ECGs, and blood collection for clinical laboratory assessments) should correspond to that scheduled visit. Assessments at an EDV that occurs on a day between two scheduled visits will be assigned to the next scheduled visit. All other assessments (such as questionnaire and PK samples) collected on an EDV will not be mapped.

In the by-visit summary tables, only nominal (scheduled) visits where the assessment is scheduled will be included. For example, if a subject had an EDV after Visit 4 and before Visit 5, the applicable assessments will be mapped to Visit 5 (ie, the next scheduled visit). Vital signs and ECGs collected at the EDV will be summarized under Visit 5 in the by-visit summary tables. However, Visit 5 will not be included in the by-visit summary tables for the clinical laboratory assessments as lab assessments are not scheduled on Visit 5. Unscheduled visits will not be mapped to scheduled visits. In the subject listing, data will be presented under the actual visits, including EDV and unscheduled visits.

Seizure data collected by diary are associated with periods defined within the study and as such need no mapping to visits. If a subject withdraws between visits an effort is made to recover all diary records for use in calculation of seizure frequencies.

### **3.2.5 Last Visit during the Treatment Period**

The Last Visit for an assessment is the last non-missing assessment during the Treatment Period. All scheduled and unscheduled assessments within the Treatment Period will be considered. Last Visit will be determined separately each study assessment. Last Visit during the Treatment Period will be included in the by-visit summary unless noted otherwise.

## **3.3 Definition of Baseline values**

### **3.3.1 Baseline for variables based on seizure count**

Baseline values for seizure frequency variables will be derived from diary data recorded by the subject during the 4-week Baseline Period. This diary is collected at the Baseline Visit (Visit 2, Day 1). The Baseline value will be the seizure frequency per 28 days during the Baseline Period and is defined as the number of seizures standardized to a 28-day baseline period. It is computed for each subject as the number of seizures recorded over the subject's baseline diary period, divided by the subject's total number of non-missing days in that period, multiplied by 28. See details for calculation of seizure frequency in Section 8.1.1.1.

### **3.3.2 Baseline for other variables**

Unless otherwise specified, the last valid measurement before the first study medication administration will be used as the Baseline value, including the pre-dose assessments on the day of Visit 2. Unless otherwise stated, if a Baseline visit measurement is missing, and a Screening visit measurement is available, the most recent Screening value will be utilized as Baseline. Both scheduled and unscheduled Screening visits will be considered. If a scheduled Baseline assessment is taken on the same day as first administration of study medication and no time is collected, it will be assumed to have been taken prior to study medication. The time point used

for Baseline will be determined separately for each variable. An exception is blood pressure, where a complete set of both systolic and diastolic blood pressure should be selected for baseline. Baseline values for PK evaluations included in this SAP is defined in Section 9.

### **3.4 Protocol deviations**

Important protocol deviations (IPD) are those deviations from the protocol identified by the study team as important which will be summarized in the clinical report, in accordance with ICH E3. The criteria for identifying important protocol deviations will be defined within the appropriate protocol-specific document at study start. All protocol deviations will be reviewed periodically through the study as part of the ongoing data cleaning process and those identified as important will be documented prior to unblinding and integrated into the clinical database.

### **3.5 Analysis sets**

Primary and secondary efficacy endpoints will be analyzed using the Full Analysis Set (FAS). Sensitivity analysis on the primary endpoints will be performed using the Per Protocol Set (PPS). Safety variables will be analyzed using the Safety Set (SS). Pharmacokinetic data summaries will use the PK Per Protocol Set (PK-PPS) or AED PK Per Protocol Set (AED-PK-PPS).

These analysis sets are described below.

#### **3.5.1 Enrolled Set**

The Enrolled Set (ES) consists of all subjects who have given informed consent.

#### **3.5.2 Randomized Set**

The Randomized Set (RS) consists of all subjects randomized into the study; this includes all subjects who have a randomization number issued by the IRT, even if misrandomized.

#### **3.5.3 Safety Set**

The SS consists of all subjects who were administered at least 1 dose or a partial dose of IMP, based on the first dose date from the First Administration of Study Medication CRF. The SS will be used to summarize and analyze all safety variables. In case of dosing administration error, summaries and analyses using the SS will be conducted according to actual treatment administered.

#### **3.5.4 Full Analysis Set**

The Full Analysis Set (FAS) consists of all subjects in the RS who were administered at least 1 dose or a partial dose of IMP and have Baseline and at least 1 post-Baseline seizure frequency data during the Treatment Period. In case of dosing administration error, or change in treatment dose, summaries and analyses will be conducted according to randomized treatment and not the actual treatment received. The FAS will be the primary analysis set for all efficacy summaries and analyses.

#### **3.5.5 Per Protocol Set**

The Per Protocol Set (PPS) is a subset of the FAS, consisting of those subjects who had at least 1 post-Baseline efficacy measurement and who had no major protocol deviation affecting the primary efficacy variable, as confirmed during a pre-analysis data review meeting, conducted prior to study unblinding. Criteria will be developed and documented (in a separate document)

prior to study unblinding to identify subjects with major protocol deviations so that they may be excluded from the PPS. The PPS will be used for sensitivity analyses of selected efficacy endpoints as described later in the SAP.

### **3.5.6 Completer Set**

The Completer Set is a subset of the FAS, consisting of those subjects who completed the 16-week treatment period.

### **3.5.7 Other analysis sets**

#### **3.5.7.1 Pharmacokinetic Set**

The Pharmacokinetic Set (PKS) consists of those subjects who provide at least 1 PSL plasma concentration measurement. Note that it is possible for a subject in the PK-Set to have missing data for some evaluations (such as of the primary [REDACTED]).

#### **3.5.7.2 Pharmacokinetic Per-Protocol Set (PK-PPS)**

A PK Per Protocol Set (PK-PPS) will be a subset of the PKS and identified for active treatment groups, which would exclude subjects or PK sample data points with major deviations that could impact PK evaluations e.g. when there is evidence that the sample collected is not at steady-state due to missing doses, dose alterations or interacting concomitant medications, etc. Subjects or PK sample data points to be excluded from this PK-PPS, will be identified during a pre-analysis data review.

#### **3.5.7.3 AED Pharmacokinetic Per-Protocol Set (AED-PK-PPS)**

An AED PK Per Protocol Set (AED-PK-PPS) will be identified, which would exclude subjects or AED PK sample data points with major deviations that could impact AED PK evaluations. Subjects or AED PK sample data points to be excluded from this AED-PK-PPS, will be identified during a pre-analysis data review.

## **3.6 Treatment assignment and treatment groups**

At Baseline, eligible subjects will be randomly assigned to treatment regimens as described in Section 2.3. Prior to unblinding, the study team should identify and review all cases in which subjects received an incorrect study drug (dosing errors resulting in treatment crossover). Note that while dispensing errors can be identified prior to unblinding, actual treatment crossovers can only be identified via IRT report (only identifying the subject number), or after unblinding.

The FAS will be the primary analysis set for all efficacy summaries and analyses. Treatment crossover Subjects (including any subjects with dosing errors) will be analyzed for efficacy according to their randomized treatment assignment and not the actual treatment received.

Safety analyses will be based on the SS. It is expected that subjects will receive the randomized treatment and be analyzed according to that assigned treatment. However, if a subject were to experience a dosing error resulting in treatment crossover, incorrectly treated subjects will be evaluated during the blinded data evaluation meetings to assess the potential impact of such cases and any special considerations for statistical analyses.

### **3.7 Sites pooling strategy**

Since “site” per se is not considered as a factor in the planned analyses there is no strategy in place for pooling data from sites with low number of patients to another particular site. Data will be combined across all sites within region, according to the specified analysis. To ensure at least 5 subjects in each region in the FAS at each treatment group, Japan will be pooled with North America to form a non-Europe region for the efficacy analyses.

### **3.8 Coding dictionaries**

All prior and concomitant medications other than study drug will be classified by World Health Organization WHO Anatomical Therapeutic Chemical (ATC) Classification, presenting Anatomical Main Group (ATC Level 1), Pharmacological Subgroup (ATC level 3); and preferred term, using Version SEP/2015 or higher of the World Health Organization Drug Dictionary (WHO-DD). Coding will be performed in accordance with UCB standard operating procedures (SOP).

Medical history and AEs will be coded by primary system organ class (SOC), high level term (HLT) and preferred term (PT) using version 19.0 or higher of Medical Dictionary for Regulatory Activities (MedDRA®) according to UCB Standard Operating Procedures (SOP).

### **3.9 Changes to protocol-defined analyses**

Not applicable; there have not been any changed to protocol defined analyses.

## **4 STATISTICAL/ANALYTICAL ISSUES**

General statistical and analytical issues are provided in the following sections.

### **4.1 Adjustments for covariates**

The primary and selected efficacy analyses will be adjusted for baseline log-transformed seizure frequency and for the stratification factors:

- Current use of AEDs with binding to SV2A proteins (LEV and/or brivaracetam): Yes or No
- Geographical Region: Investigative sites have been identified in the following regions and countries at the time of this SAP amendment. More regions and/or countries may be identified and will be included in the analyses in accordance to the randomization strata:
  - Europe (Australia, Belgium, Bulgaria, Czech Republic, France, Germany, Hungary, Italy, Lithuania, Poland, Portugal, Slovakia, Spain, Turkey, and United Kingdom)
  - North America (Canada, Mexico, and United States)
  - Asia (Japan)

To ensure at least 5 subjects in each region in the FAS at each treatment group, Japan will be pooled with North America to form a non-Europe region for the efficacy analyses.

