The 16-week Treatment Period includes a 3-week Titration Period followed by a 1-week Stabilization Period and a 12-week Maintenance Period. Four weeks after the Screening Visit (Visit 1), subjects will return to the clinic for the Baseline Visit (Visit 2, Day 1). Subjects who continue to fulfill the inclusion and exclusion criteria will be randomized to 1 of the 5 treatment arms in a 1:1:1:1:1 ratio (random permuted blocks) to ensure the balance to 1 of the 5 treatment arms. Randomization will be stratified by current use of AEDs with binding to SV2A proteins (LEV or brivaracetam) and by region (North America, Europe, and Asia) at the time of randomization.

After the Baseline Visit (Visit 2), subjects will return to the clinic for regular visits for the remainder of the Titration Phase. Investigational medicinal product will be increased approximately every 3 to 7 days depending on treatment arms (refer to [Table 7-1](#) for details). Subjects will be instructed to take the IMP in 2 equally divided doses, approximately 12 hours apart in the morning and evening.

During the entire 16-week Treatment Period, the dose of concomitant AEDs and the settings for neurostimulation devices must remain stable. The dose of IMP should remain stable during the Maintenance Period.

Subjects who cannot tolerate IMP prior to Week 3 will be withdrawn from the study. For subjects with tolerability issues experienced at their target dose, one fallback option to a predefined dose based on the randomized dose (see [Table 7-2](#)) will be allowed during the Stabilization Period and at least 2 days prior to start of maintenance (Visit 4). The Study Physician or delegate should be consulted prior to use of the fallback option and the date as well as the reason for fallback will be recorded in the source documents and in the electronic Case Report form (eCRF).

Fallback may be managed via an unscheduled visit. Fallback IMP packs will be allocated via the Interactive Response Technology (IRT). After fallback, the dose will be kept stable for the rest of the Maintenance Period. Further dose changes (ie, titration) are not allowed. Subjects, who are not able to tolerate the IMP during titration and after the fallback, will be tapered off IMP in a blinded fashion and will be withdrawn from the study.

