7.9 Blinding

This is a study with a double-blind study during all study periods (ie, Titration Period, Treatment Period, and Taper/Conversion Period). At the start of the Titration Period, subjects will be randomized to 1 of the 5-treatment arms in a 1:1:1:1:1 ratio (random permuted blocks).

Randomization will be stratified by current use of AEDs with binding to SV2A proteins (LEV or brivaracetam) and region (North America, Europe, and Asia) at the time of randomization.

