13.3.1 Analysis of the primary efficacy variable

13.3.1.1 Analysis of the primary efficacy variable for the US FDA, PMDA, and other regulatory authorities not specified in Section 4.1.1.2

Pairwise comparisons of 400mg, 200mg and 100mg dose groups versus placebo will be carried out using the analysis model below. Type 1 error will be controlled by the Hochberg step-up procedure within SAS® Proc Multtest. If all the results of the pairwise comparisons are statistically significant then the 50mg dose group will be compared to placebo.

For the US FDA, PMDA, and other regulatory authorities not specified in Section 4.1.1.2, the primary efficacy variable is the change in log-transformed observable focal-onset seizure frequency from Baseline, over the 12-week Maintenance Period. The 28-day Baseline and post-Baseline (maintenance) seizure frequency will be transformed with the natural logarithm, specifically $\ln(x+1)$, where x represents the 28-day seizure frequency. The transformed seizure frequency data will be analyzed using analysis of covariance (ANCOVA) with treatment group

as the main factor, Baseline log-adjusted seizure frequency as a continuous covariate, and Baseline SV2A use and Region as categorical factors. Pairwise contrasts will be constructed to compute estimated effects of each dose from placebo.

All pairwise analyses of the primary efficacy variable will be repeated on the PPS.

13.3.1.2 Analysis of the primary efficacy variable for EMA and regulatory authorities who reference EMA

For EMA and regulatory authorities who reference EMA, the primary efficacy variable will be the 75% responder rate in observable focal-onset seizures during the Maintenance Period and will be analyzed using logistic regression with factors for treatment group, Baseline seizure frequency, Region, and Baseline SV2A use. If there are issues with convergence, Baseline SV2A use will be dropped.

The same methodology carried out in Section 13.3.1.1 will be applied to the pairwise analyses.

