### **6.2 Other Baseline characteristics**

- Randomization is stratified by region (Europe, North America, and Asia), and by current use of AEDs with binding to SV2A proteins, such as LEV and/or BRV (yes or no). The percentages of subjects in each stratum for each stratification factor will be summarized for the RS.
- Lifestyle information (alcohol and illicit drug use) obtained at the Screening Visit (Lifestyle CRF) will be listed for the RS. These variables will be summarized descriptively (number and percent of subjects in each category) for the SS.

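### SAP 4.1 pools Japan with North America in the efficacy models to meet a per-arm minimum that an additive region factor does not need; the cost is small and conservative, and the three randomized regions could be kept almost free of charge

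*SAP*

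**What the plan says.** Protocol 5.1 stratifies the randomization by current use of SV2A-binding AEDs "and by region (North America, Europe, and Asia) at the time of randomization"; Protocol 7.9 says the same, and SAP 6.2 restates the three regions. Protocol 13.3.1.1 specifies the log-frequency ANCOVA with "Baseline SV2A use and Region as categorical factors", and Protocol 13.3.1.2 puts Region in the logistic model for the 75% responder rate. Neither section mentions pooling or fixes the levels of Region.

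SAP 4.1 says the primary and selected efficacy analyses are "adjusted for baseline log-transformed seizure frequency and for the stratification factors", and that further regions or countries "will be included in the analyses in accordance to the randomization strata". The same section, like SAP 3.7, then says that "Japan will be pooled with North America to form a non-Europe region for the efficacy analyses". The reason given is a floor of five FAS subjects per region in each treatment group. SAP 8.1.2.1 (ANCOVA), 8.1.2.3 (logistic) and 8.3.2.1 (MMRM) all carry Region as Europe or Non-Europe, with no treatment-by-region term. If a primary model does not converge, SAP 8.1.2.1 and 8.1.2.3 drop Region first. SAP 3.9 says "there have not been any changed to protocol defined analyses".

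**The concern.** SAP 4.1 does not do what it announces: the region factor in the models is coarser than the region factor used to randomize. The stated reason belongs to analyses that estimate something within each region-by-arm cell. An additive region term borrows across arms and needs only enough subjects in the region overall.

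Stratified randomization balances the arms within Japan and within North America. If outcomes differ between the two, that balance removes the difference from the true sampling error of a treatment contrast. A model that cannot see the split still counts the difference as noise, so its standard errors are a little too wide for the design. What is at stake is a small amount of precision and agreement between design and analysis, in a trial whose log-frequency primary variable is designated for the PMDA among others.

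**Working it through.** **The plan's own figure.** Protocol 13.8 gives 80 per arm, 90% power, two-sided 5%, SD 0.985 and log-reductions of 0.195 (placebo) and 0.670, 0.754 and 0.780 (100, 200 and 400 mg bid). A simulation of the three-comparison Hochberg rule with a shared placebo arm (200,000 runs) gives 91.3% power for 400 and 200 mg bid, or 200 and 100 mg bid, and 90.3% for 400 and 200 mg bid alone. The figure reproduces.

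**Does the additive ANCOVA need five per cell?** Take 400 subjects with only 10 in Asia, split 2/1/0/4/3 over the arms (assumed). The design matrix with intercept, four dose terms and three-level region has full rank, 7 of 7. Standard errors against placebo are 0.1558-0.1560, compared with 0.1557 for two-level region. The extra level costs less than 0.2% in standard error and one degree of freedom, even with an empty cell.

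**Size of the effect of pooling.** The documents give no counts by region, so these inputs are assumptions shown as a range. With Asia share a, North America share b and a Japan-North America difference d on the log scale:

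- added residual variance, as a share = d² × ab/(a+b) ÷ 0.985², with 0.985² = 0.970
- standard-error inflation = √(1 + share) − 1

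| a | b | ab/(a+b) | d | added variance | standard error |
|---|---|---|---|---|---|
| 0.05 | 0.30 | 0.0429 | 0.3 | 0.4% | 0.2% |
| 0.05 | 0.30 | 0.0429 | 0.5 | 1.1% | 0.55% |
| 0.08 | 0.30 | 0.0632 | 0.3 | 0.6% | 0.3% |
| 0.08 | 0.30 | 0.0632 | 0.5 | 1.6% | 0.8% |

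With d = 0 the inflation is nil.

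**Simulation with blocks stratified by region** (Europe 220 of 400, Asia 10 to 40, difference 0 to 1.0, all assumed; 2,500 null and 1,500 alternative runs per scenario):

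- Type I error of one comparison at 0.05 is 0.036-0.054 with two levels and 0.042-0.056 with three.
- The mean standard error is 0-4% larger with two levels. The extreme is 0.1621 against 0.1558, with 40 Asian subjects and a difference of 1.0. The formula agrees: a = 0.10, b = 0.35, share = 0.0778 ÷ 0.970 = 8.0%, standard error 3.9%.
- In that extreme case the empirical SD of the estimate is nearly the same either way (0.1556 and 0.1552). The pooled model therefore overstates its error rather than estimating less well.
- Power is 89-92% with two levels and 90-92% with three. The gain is about 0 points with no regional difference and 1-2 points with a difference of 1.0.

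**Logistic model.** Here a sparse region can matter, but through its total. At the Protocol 13.8 rates, the chance of no 75% responder with one Asian subject per arm is 0.879 × 0.767 × 0.699 × 0.668 × 0.658 = 20.7%. With two per arm (10 in all) it is 0.207² = 4.3%; with 15 in all 0.9%; with 20, 0.2%.

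**By-arm imputation.** SAP 8.1.2.2.2.1 fits the missing-at-random regression separately in each arm. In the 2/1/0/4/3 example, the arm with no Asian subject has rank 2 of 3, so three-level region cannot be estimated there.

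**The case against.** The strongest reply is that collapsing a sparse stratum is common practice and errs on the safe side. The pooling is pre-specified and logged in SAP Amendment 2. The protocol names only Region, without levels, and Protocol 13 leaves full details to the SAP. The Japan-specific reader is served by the SAP addendum, which repeats all tables for Japan and non-Japan. All of that stands, so a reader who infers a concealed change to the protocol model goes further than the documents allow. What remains is that SAP 4.1 promises adjustment for the strata and SAP 3.9 does not mention the coarser factor.

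A reader might also infer that the five-subject floor matters only for the region subgroup display and the by-arm imputation. That is too strong. Region is a stratum in the exact conditional logistic models (SAP 8.1.2.3, 8.3.2.5, 8.3.2.10 and 8.3.2.16), where a small stratum with no responder contributes nothing. In the primary logistic model, a failure to converge removes Region altogether, and pooling lowers that risk. Neither reason extends to the ANCOVA or the MMRM.

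Larger effect sizes can be produced, but only from unlikely inputs. A regional difference of 0.8 would exceed the largest assumed drug effect, 0.780 − 0.195 = 0.585. An Asian share of 8% would be 32 of 400, about 6.4 per arm, which would usually meet the floor of five without pooling. The stated reason therefore points to a smaller stratum.

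**Conclusion.** The point holds as a low-cost improvement, not as an error that threatens a conclusion. The reason given for pooling does not apply to the additive ANCOVA and MMRM, and the region factor there does not match the randomization. The standard error is about 0.2-0.8% too wide if Asia is 5-8% and North America 30% of subjects and the two differ by 0.3-0.5 log units; all of these are assumptions. With no difference there is no effect.

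It would be tempting to conclude that the primary test is invalid or that the trial loses meaningful power. The calculations do not support either: type I error shows no inflation, and even a difference of 1.0 costs only 1-2 points of power. Nothing in the documents shows that Japan and North America differ.

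**What to change.** - **ANCOVA and MMRM** (SAP 8.1.2.1 and 8.3.2.1): use the three-level randomization region as a main effect.
- **Primary logistic model** (SAP 8.1.2.3): use three levels as well. If it does not converge, or Asia has no responders, go to Europe/Non-Europe first, and only then drop Region.
- **Keep Europe/Non-Europe** for the region subgroup analysis, the exact conditional logistic models and the multiple-imputation analyses. SAP 8.1.2.2.2.1, 8.1.2.2.2.2 and 8.1.2.4.3 now analyse the imputed data with the primary model. They should state that imputation and analysis use the same region levels: two in both, or three in both where estimable.
- **SAP 3.7 and 4.1**: limit the pooling rule to those analyses.
- **SAP 3.9**: record any pooling that remains in a protocol-defined model.

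The cost is wording in these sections and one degree of freedom in the ANCOVA. No further data are needed.
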